13.4 Other Baseline Characteristics

The following baseline characteristics will be reported for this study:

- ECOG PS: 0 or 1
- c-Met Status: Immunohistochemistry (IHC) 0, IHC 1+, IHC 2+, IHC 3+
- c-Met Status: In Situ Hybridization (ISH): ISH+, ISH-
- HGF: Cancer-Associated Fibroblast (CAF)
- HGF: Cytoplasmic
- Alcohol use status: Never used, Regular user, Occasional user, or Former user
- Nicotine use status: Never used, Regular user, Occasional user, or Former user
- Height (cm)
- Weight (kg)
- Body Mass Index (kg/m²)
- Vascular invasion and/or extrahepatic spread: Presence or Absence
- AFP elevation at baseline: > 200 IU/mL or < 200 IU/mL
- Prior local-regional therapy: Yes or No
- Albumin-Bilirubin (ALBI) Grade (1): 1, 2, or 3

Specifications for computation:

- ALBI Grade (1):
 - O Calculate the linear predictor y: $y = (log_{10}(bilirubin) * 0.66) + (albumin * -0.085)$ where bilirubin is in μ mol/L and albumin is in g/L
 - o Compare y to the following cut points:

■ ALBI Grade 1: $y \le -2.60$

■ ALBI Grade 2: $-2.60 < y \le -1.39$

■ ALBI Grade 3: y > -1.39

• BMI (kg/m^2) = weight $(kg)/[height (m)]^2$

13.5 Prior Anti-Cancer Therapies

Information related to prior anti-cancer therapies were collected on the "Prior Anti-Cancer Drug Therapies Details", "Prior Anti-Cancer Radiotherapy Details", "Prior anti-Cancer Local-Regional Therapy Details", and "Prior Anti-Cancer Surgery Details" eCRF pages. Prior anti-cancer therapy related data will be listed.

14 Previous or Concomitant Medications/Procedures

Analysis Set: ITT/SAF

Summaries for previous and concomitant medications/procedures will be presented by dose level and overall.

Concomitant treatments are medications, other than trial medications, taken by subjects any time during the on-treatment period.

Previous medications are medications, other than trial medications and pre-medications for trial treatment, which are started before first administration of trial treatment.

Previous and concomitant medications will be summarized from the "Concomitant Medications Details" eCRF page.

In cases where date values do not allow unequivocal allocation of a medication to concomitant or previous medication, the medication will be considered as both a concomitant and previous medication.

Summaries of previous and concomitant medications will include the number and percentage of subjects by ATC classification level 2 and PT, as given from the latest version of the World Health Organization Drug Dictionary (WHO-DD). A subject will be counted only once within a given ATC class and within a given PT, even if he/she received the same medication at different times. If any previous or concomitant medication is classified into multiple ATC classes, the medication will be summarized separately under each of these ATC classes. Summary tables will be sorted alphabetically by ATC class and PT. In case any specific medication does not have an ATC classification level 2 coded term, it will be summarized under the "Unavailable ATC classification" category.

All **concurrent procedures**, which were undertaken any time on trial, were collected on the eCRF page "Concomitant Procedure Details". The number and percentage of subjects with any

concurrent procedure, a concurrent procedure starting prior to the first dose of treatment, and a concurrent procedure starting after the start of treatment but within 33 days after the last dose of trial treatment will be presented.

15 Treatment Compliance and Exposure

Analysis Set: ITT/SAF

All dosing calculations and summaries will be based on the "Cohort Treatment MSC2156119J Administration Details" eCRF page.

Handling of missing data:

If the actual dose is missing, the planned dose level as entered in the eCRF will be used.

Cumulative Dose

The cumulative dose (mg) of tepotinib per subject is the sum of the actual dose levels that the subject received (i.e. total dose administered [mg]).

Duration

For the purposes of deriving dose intensity, the duration of therapy (in weeks) during the trial is defined as:

Duration=
$$\left(\frac{\text{last dose date - first dose date} + 1}{7}\right)$$

The duration of therapy (in months) during the trial is defined as:

Duration=
$$\left(\frac{\text{last dose date - first dose date} + 1}{30.4375}\right)$$

Dose Intensity

The dose intensity and the relative dose intensity will be calculated for each subject across all cycles assuming a 3-week cycle duration. Dose intensity (mg/cycle) is defined as

Dose intensity=
$$\left(\frac{\text{Cumulative dose}}{(\text{duration of therapy (in weeks)})/3}\right)$$

Relative Dose Intensity

Relative dose intensity, a measure of compliance, is defined as the dose intensity divided by the planned dose per cycle.

Number of Cycles Completed

The number of cycles a subject completed will be calculated as follows:

Number of cycles completed = floor
$$\left(\frac{\text{(last dose date - first dose date + 1)}}{21}\right)$$

Number of Cycles Initiated

The number of cycles a subject initiated will be calculated as follows:

Number of cycles initiated = ceiling
$$\left(\frac{\text{(last dose date - first dose date + 1)}}{21}\right)$$

The following will be summarized:

- Total number of initiated vs. completed cycles on treatment
- Duration (months)
- Cumulative dose (mg)
- Dose intensity (mg/cycle)
- Relative dose intensity (%) during Cycle 1 and overall

Dose reductions

A dose reduction is defined as a change from the planned dose level to one of the 2 lower dose levels below the recommended phase II dose (RP2D) (See CTP Section 6.2.3). The number of subjects with at least one dose reduction will be summarized by frequency and percentage per planned dose level. The minimum dose of the trial treatment will be derived per subject and categorized according to categories of reduced to 300 mg and reduced to 200 mg.

Dosing Interruptions

A dose interruption is defined as having missed 1 or more planned daily doses. Dosing interruptions will be summarized by planned dose level for the number of subjects with an interruption lasting either 1-2 days, 3-7 days, 8-14 days, and greater than 14 days (The longest interruption and cumulative days of interruption are summarized for each subject.)

Investigational Medicinal Product (IMP) Allocation

A listing of batch numbers of IMP and the subjects receiving IMP from the specific batch will be presented.

16 Endpoint Evaluation

16.1 Primary Endpoint Analysis

Analysis Set: DLT

The primary endpoint of this study is the incidence of DLTs occurring during Cycle 1. DLTs are collected on the "Adverse Events Details" form on the eCRF and are recorded as the answer ("Yes", "No", or "Not Applicable") to "Is this adverse event a dose limiting toxicity?" A DLT is defined as a toxicity of interest judged to be related to tepotinib by the investigator and/or the sponsor using the National Cancer Institute – Common Terminology Criteria for Adverse Events (NCI-CTCAE) version 4.0. Per the NCI-CTCAE, a DLT is defined as any of the following toxicities at any dose level and judged to be related to the trial treatment by the investigator and/or the sponsor:

- Grade 4 neutropenia for more than 7 days
- Grade ≥ 3 febrile neutropenia for more than 1 day
- Grade 4 thrombocytopenia or Grade 3 thrombocytopenia with nontraumatic bleeding
- Grade ≥ 3 uncontrolled nausea/vomiting and/or diarrhea despite adequate and optimal treatment for more than 3 days
- Grade ≥ 3 any nonhematological AE except the aforementioned gastrointestinal events and alopecia; however, a DLT is defined specifically for the following cases:
 - o Grade ≥ 3 liver AE requiring a recovery period of more than 7 days to the baseline or to Grade 1 or less (This criterion is not limited to the liver function tests. Other liver AEs such as jaundice or hepatic encephalopathy suggestive of liver failure should also be considered.)
 - Grade \geq 3 lipase and/or amylase elevation with confirmation of pancreatitis, either based on clinical or radiological signs will be considered as a DLT. An isolated lipase and/or amylase elevation of \geq Grade 3 without clinical or radiological evidence of pancreatitis will not be classified as a DLT.

AEs assessed by the investigators to be exclusively related to the subject's underlying disease or medical condition/concomitant treatment are not considered as DLTs.

The DLT summary table will present the following for the DLT analysis set:

- the number and proportion of subjects who experienced a DLT during Cycle 1 with corresponding two-sided exact Clopper Pearson (2) 90% confidence intervals (CIs)
- DLTs during Cycle 1 by SOC and PT

There will be no imputation of missing data for the DLT variable. A listing of DLT adverse event data will include subject identifier, dose level, and all relevant variables from the Adverse Event Details eCRF page.

16.2 Secondary Endpoint Analyses

Analysis Set: ITT/SAF

Tumor assessment will be performed by the investigator primarily according to the RECIST version 1.1 and secondarily according to the modified RECIST (mRECIST) for HCC (see CTP appendices J and K). The baseline tumor assessment is scheduled to be performed during the screening period. Tumor response evaluations will then be assessed by computed tomography (CT) or magnetic resonance imaging (MRI), whichever was used at the baseline tumor assessment, at the end of every 2 cycles (i.e. before the start of Cycles 3, 5, 7, 9, 11, 13, and every 4 cycles thereafter until PD). Tumor assessments will be performed at the end of treatment visit for subjects whose last tumor assessment was performed \geq 6 weeks prior.

16.2.1 Efficacy Endpoints

16.2.1.1 Time to Progression (TTP)

TTP will be measured as the time (in months) from the date of first trial treatment administration to the date of radiological confirmation of PD performed according to RECIST Version 1.1. TTP will be censored at the date of last adequate tumor assessment for subjects that do not experience progression or subjects that experience progression after 2 or more subsequent missing tumor assessments. Subjects that are missing a baseline tumor assessment and/or all post-baseline tumor assessments will be censored at the first date of study drug administration.

The date of event/censoring is defined as follows:

Status		Censoring	Date of event / censoring
Progressed	Within two subsequent scheduled tumor assessments after last response assessment of CR, PR or SD or first study drug administration	Event	Date of PD
	Otherwise	Censored	Date of last tumor assessment with outcome CR, PR or SD or date of first study drug administration, whatever is later

Tepotinib Second-Line HCC EMR 200095-005 Phase Ib CTR SAP Version 1.0

Didn't progress	Censored	Date of last tumor assessment with outcome CR, PR or SD or date of first study drug administration, whatever is later
-----------------	----------	---

TTP (months) = (date of PD/censoring – date of first trial treatment administration + 1)/30.4375

The number and percentage of individuals with progression will be presented per dose level. Kaplan-Meier (i.e. product-limit) estimates of the minimum, maximum, and median TTP will be presented overall along with 90% CIs for the median calculated according to Brookmeyer and Crowley (3). In addition, the pattern of censoring will be summarized overall (e.g., censoring due to death, study withdrawal, lost to follow-up, censoring due to data cut-off).

The number of subjects at risk for progression vs. those who have experienced progression along with Kaplan-Meier estimates of survival probability at 3, 6, and 12 months will be estimated with corresponding 90% CIs derived using the log-log transformation according to Kalbfleisch and Prentice (4) (i.e. conftype = loglog default option in SAS LIFETEST procedure).

A Kaplan-Meier plot of TTP and a listing of relevant TTP data will be provided.

16.2.1.2 Progression Free Survival (PFS)

PFS time is defined as the time from the date of first treatment administration to

- o the date of the first documentation of objective PD or
- o death due to any cause,

whichever occurs first.

PFS time will be censored at the date of last adequate tumor assessment for subjects who

- o do not have an event (PD or death within 12 weeks of last tumor assessment) or
- o have an event after two or more subsequent missing tumor assessments.

PFS time will be censored on the date of first study treatment for subjects who do not have

- o a baseline tumor assessment or
- o any post-baseline tumor assessments,

unless death occurred on or before the time of the second planned tumor assessment, in which case the death will be considered an event.

The date of event/censoring is defined as follows:

Status		Censoring	Date of event / censoring
Progressed or died	Within two subsequent scheduled tumor assessments after last response assessment of CR, PR or SD or first study drug administration	Event	Minimum(Date of PD, Date of death)
	Otherwise	Censored	Date of last tumor assessment with outcome CR, PR or SD or date of first study drug administration, whatever is later
Neither progressed nor died		Censored	Date of last tumor assessment with outcome CR, PR or SD or date of first study drug administration, whatever is later

PFS (months) = (date of event/censoring – date of first trial treatment administration $+ \frac{1}{30.4375}$

The analysis of PFS will be performed using Kaplan-Meier methods with the same approach for TTP described above.

The primary analysis of PFS will be based on RECIST Version 1.1 criteria. The primary analysis of PFS will be repeated based on mRECIST for HCC as an exploratory analysis.

16.2.1.3 Overall Survival (OS) Time

OS time is defined as the time (in months) from the date of first treatment administration to the date of death.

The date of event/censoring is defined as follows:

Survival Status	Source	Censoring	Date of event/censoring
Died	Death CRF	Event	Date of death
Alive (no date of death)	To be determined as defined in section 11	Censored	Last date known to be alive (defined in section 11)

OS (months) = $\frac{\text{date of death/censoring} - \text{date of first trial treatment administration} + 1)/30.4375$

The analysis of OS will be performed using Kaplan-Meier methods with the same approach for TTP described above.

16.2.1.4 Best Overall Response

The best overall response (BOR) is the best response recorded from the start of treatment until disease progression. The BOR across all time points will be established applying the confirmation criteria based on RECIST 1.1, taking confirmation requirements into account as presented in Table 16.1. CR/PR may be claimed only if the corresponding criteria in Table 16.1 are met at a subsequent time point (28 days later). The time gap of two consecutive tumor response evaluations is the difference of two dates (i.e. the earliest scan date of target lesions associated with each assessment visit). SD may be claimed only if the SD criteria are met at least once after first administration at a minimum interval of 6 weeks. The time interval for SD will be calculated as (date of overall response - first dosing date of any of trial drug +1). The confirmation of response must not necessarily be at the next scan, but could be at any subsequent scan before PD. For instance, if a subject has PR-SD-PR or PR-NE-PR at consecutive tumor assessments, the BOR would qualify for PR (1). The number and percentage of subjects with BOR of CR, PR, SD, PD and not NE (not evaluable) will be summarized by the following:

- Dose level and overall
- c-Met status (IHC), dose level, and overall
- c-Met status (ISH), dose level, and overall

A figure displaying the BOR for each subject along with their percent change from baseline in AFP value will be displayed against time (weeks) in a line plot by the following baseline categories: < 200 ug/L, >= 200 ug/L, < 400 ug/L, and >= 400 ug/L. The BOR for each subject as assessed by RECIST 1.1 will be indicated in the figure.

A swimmer plot summarizing exposure information and response data will be presented by dose level and c-Met status (IHC/ISH). The BOR for each subject as assessed by RECIST 1.1 will be indicated in the figure.

Table 16.1 – Best Overall Response when Confirmation of CR and PR is Required

Overall response	Overall response	BEST overall response
First time point	Subsequent time point	
CR	CR	CR
CR	PR	SD, PD or PR ^a
CR	SD	SD provided minimum criteria for SD duration met, otherwise PD
CR	PD	SD provided minimum criteria for SD duration met, otherwise PD

Tepotinib Second-Line HCC EMR 200095-005 Phase Ib CTR SAP Version 1.0

CR	NE	SD provided minimum criteria for SD duration met, otherwise NE
PR	CR	PR
PR	PR	PR
PR	SD	SD provided minimum criteria for SD duration met, otherwise NE
PR	PD	SD provided minimum criteria for SD duration met, otherwise PD
PR	NE	SD provided minimum criteria for SD duration met, otherwise NE
SD	Any	SD provided minimum criteria for SD duration met, otherwise PD
PD	Any	PD
NE	NE	NE

CR = complete response, PR = partial response, SD = stable disease, PD = progressive disease, and NE = not evaluable.

Objective tumor response

Objective tumor response will be evaluated by the objective response rate (ORR). The ORR is the proportion of subjects having achieved a BOR of CR or PR. The ORR will be established applying the criteria based on RECIST 1.1.

ORR will be summarized along with corresponding two-sided exact Clopper-Pearson (2) 90% CIs by the following:

- Dose level and overall
- c-Met status (IHC), dose level, and overall
- c-Met status (ISH), dose level, and overall

Disease Control

Disease control will be evaluated by the disease control rate, defined as the proportion of subjects having achieved a BOR of CR, PR, or SD.

Disease control rate will be summarized along with corresponding two-sided exact Clopper-Pearson (2) 90% CIs by the following:

^a If a CR is truly met at first time point, then any disease seen at a subsequent time point, even disease meeting PR criteria relative to baseline, makes the disease PD at that point (since disease must have reappeared after CR). Best response would depend whether minimum duration for SD was met. However, sometime CR may be claimed when subsequent scans suggest small lesions were likely still present and in fact the subject had PR, not CR at the first time point. Under these circumstances, the original CR should be changed to PR and the best response is PR.

- Dose level and overall
- c-Met status (IHC), dose level, and overall
- c-Met status (ISH), dose level, and overall

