# 7.1.3.7 Cycle 3 Day 1 (and Day 1 of All Subsequent Cycles)

The frequency of visits will be every 3 weeks up through Cycle 8. From Cycle 9 onward, the frequency of visits will be every 6 weeks, and after Cycle 13, the frequency of visits will be every 12 weeks. These visits may occur within  $\pm$  5 days of Day 1 of the applicable cycle. Refer to Section 7.1.3.4 for the calculation of Day 1 of each cycle.

The following assessments and examinations will be performed on this day of each cycle for which there is a visit:

- Physical examination including body weight;
- A urine pregnancy test will be completed in women of childbearing potential before administration of the dose. If the pregnancy test is positive, it must be confirmed with a serum pregnancy test.
- ECOG PS;
- Vital signs; ECG (predose only);
- Blood samples (to assess hematology, chemistry, and coagulation);
- Urinalysis;
- Serum AFP;
- Complete tumor assessment using RECIST Version 1.1 and secondarily using mRECIST for HCC (on Day 1 of Cycles 3, 5, 7, 9, 11, 13, and every 4 cycles thereafter until disease progression or study drug discontinuation; can occur within 5 days prior to the start of each of these cycles but must be performed prior to the start of each of these cycles);
- AE assessment;
- Recording of concomitant medications/procedures;
- Tumor assessment by F-FDG PET CT scan (Cycle 3 Day 1 only);
- FHSI-8 and FACT-HP (Phase II only).

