#### Evaluation of Best Overall Response

The best overall response (BOR) is the best response recorded from the start of the trial treatment until the end of treatment taking into account any requirement for confirmation. On occasion, a response may not be documented until after the end of therapy, so protocols should be clear if posttreatment assessments are to be considered in determination of BOR. Protocols must specify how any new therapy introduced before progression will affect best response designation. The subject's BOR assignment will depend on the findings of both target and non-target disease and will also take into consideration the appearance of new lesions. Furthermore, depending on the nature of the trial and the protocol requirements, it may also require confirmatory measurement. Specifically, in non-randomized trials where response is the primary endpoint, confirmation of partial response or CR is needed to deem either one the 'BOR'.

The BOR is determined once all the data for the subject is known. Best response determination in trials where confirmation of complete or partial response IS NOT required: Best response in these trials is defined as the best response across all time points (for example, a subject who has SD at first assessment, partial response at second assessment, and PD on last assessment has a BOR of partial response). When SD is believed to be best response, it must also meet the protocol specified minimum time from baseline. If the minimum time is not met when SD is otherwise the best time point response, the subject's best response depends on the subsequent assessments. For example, a subject who has SD at first assessment, PD at second and does not meet minimum duration for SD, will have a best response of PD. The same subject lost to follow-up after the first SD assessment would be considered inevaluable.

Target Lesions	Non-target Lesions	New Lesions	Overall Response
CR*	CR	No	CR
CR	Non-CR/non-PD	No	Partial response
CR	Not Evaluated	No	Partial response
Partial response	Non-PD or not all evaluated	No	Partial response
SD	Non-PD or not all evaluated	No	SD
	Non-PD		
Not all evaluated		No	NE
PD	Any	Yes or No	PD
Any	PD	Yes or No	PD
Any	Any	Yes	PD

\* CR = complete response; SD = stable disease; and PD = progressive disease. See text for more details.

Note:

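### Phase Ib SAP Table 16.1 turns an early SD followed by a non-evaluable assessment into best response PD, against protocol Appendix J and the table's own NE rows

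*SAP*

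**What the plan says.** **Phase Ib SAP, section 16.2.1.4.** In Table 16.1 the row for first response SD and subsequent response Any reads "SD provided minimum criteria for SD duration met, otherwise PD". The same words stand in the CR / SD, CR / PD and PR / PD rows; the point here is the SD / Any row only. The CR / NE, PR / NE and PR / SD rows end differently: "SD provided minimum criteria for SD duration met, otherwise NE".

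The minimum is set in the text: "SD may be claimed only if the SD criteria are met at least once after first administration at a minimum interval of 6 weeks". The interval is counted as "date of overall response - first dosing date of any of trial drug +1".

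**Protocol Appendix J, Evaluation of Best Overall Response.** The general rule is: "If the minimum time is not met when SD is otherwise the best time point response, the subject's best response depends on the subsequent assessments". Two examples follow. One ends in PD, stating that "a subject who has SD at first assessment, PD at second and does not meet minimum duration for SD, will have a best response of" that category. In the other: "The same subject lost to follow-up after the first SD assessment would be considered inevaluable".

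**Link between the documents.** SAP section 16.2 points to protocol Appendices J and K for tumor assessment. SAP section 9 lists two changes from the protocol (baseline physical examination; relative dose intensity in place of compliance) and otherwise adopts the protocol's methods. The best-response rule is not among the changes.

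**The concern.** The SD / Any row has two outcomes, SD and PD. An early SD followed by an assessment that cannot be evaluated is therefore recorded as progression, although neither scan showed it. PD says the tumor grew on treatment; NE says the outcome is unknown. The row replaces the second statement with the first.

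The report could also disagree with itself. A subject with no documented progression is censored for TTP (SAP 16.2.1.1), where the number with progression is also tabulated by dose level. The same subject would count as PD in the best-response table.

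Best response is tabulated by dose level and by c-Met status (IHC and ISH), and it labels subjects in the AFP line plot and the swimmer plot. With at most 18 subjects, one wrong label is visible.

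**Working it through.** The plan states no figure on this point, so there is none to reproduce. The check sets the rules side by side, asks whether the case can arise on schedule, and sizes one misclassified subject.

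**1. SD / Any row against Appendix J**

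| First response SD, then | Minimum met? | Table 16.1 | Appendix J |
|---|---|---|---|
| any response short of confirmed PR or CR | yes | SD | SD |
| PD | no | PD | PD (stated) |
| NE | no | PD | not PD: depends on later assessments, and NE shows no progression |
| no further scan | no | PD if Any includes this case, otherwise no row applies | inevaluable (stated for loss to follow-up) |

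**2. SD / Any row against its sister rows, minimum not met**

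- CR / NE, PR / NE and PR / SD give NE.
- CR / PD and PR / PD give PD, and progression was observed.
- CR / SD gives PD. The table's footnote explains this: disease seen after a true CR has reappeared.
- SD / NE, under Any, gives PD with no progression and no reappearance.

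**3. Can an SD scan miss the minimum on schedule?**

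- Cycles last 21 days, so Cycle 3 Day 1 = 2 × 21 + 1 = Day 43.
- Protocol 7.1.3.7 says that the scan "can occur within 5 days prior to the start of each of these cycles", so from 43 − 5 = Day 38.
- With the SAP's formula, a scan on Day d has interval d − 1 + 1 = d days. The threshold is 6 × 7 = 42 days.
- Days 38 to 41 give 38 to 41 days and fail. Days 42 and 43 pass.
- An end-of-treatment scan is due if the last one was at least 6 weeks earlier (protocol 7.1.4). With a screening scan 28 days before Day 1, that could be as early as 1 − 28 + 42 = Day 15.

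So a subject scanned within the permitted window can have an SD that does not count. To end up as PD without progression, that subject must also have no later evaluable scan, because a later SD scan would meet the minimum.

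**4. Size of one misclassified subject.** Protocol 5.1.2 plans up to 6 subjects in the first cohort, up to 12 in the second and up to 18 in all.

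- 1/6 = 16.7%
- 1/12 = 8.3%
- 1/18 = 5.6%

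The c-Met cells within a dose level can be smaller, so one subject can weigh more there. The documents do not give those counts.

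**5. What does not move.** Objective response counts CR and PR; disease control counts CR, PR and SD. PD and NE both stay in the denominator and out of the numerator. TTP and PFS use the date of PD (for PFS also death) and do not use the best-response category.

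**The case against.** **Appendix J leaves room for a trial rule.** Its loss-to-follow-up example stands under trials that do not require confirmation, while Table 16.1 is titled for trials that do. Appendix J also hands missing assessments to the analysis plan and calls the conditions for inevaluability trial-specific. This weakens the conflict but does not remove it. Confirmation concerns CR and PR, and nothing ties the SD minimum-time rule to it. The SAP gives no reason for a stricter SD rule, does not list one in section 9, and takes the opposite line in its CR / NE and PR / NE rows.

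**The row may not cover a subject with no further scan.** The column is headed subsequent time point, and such a subject has none. That Any includes this case is an inference: the PD / Any row is the only one that could classify a subject whose single scan shows PD. The objection stands to that extent. What the row literally covers is SD then NE; what Appendix J expressly calls inevaluable is SD then loss to follow-up. On the narrower reading the second case has no rule at all, so the row needs work either way.

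**The path is narrow.** A reader might infer that subjects who stop for toxicity after one SD scan would routinely be reported as progressors. Protocol 5.5.2 does not support that: subjects who stop for reasons other than progression or withdrawal of consent keep their scan schedule until progression, consent withdrawal, new anticancer therapy or death. The remaining route is an early SD scan followed by one of those stopping reasons other than progression, by loss to follow-up, or by non-evaluable scans.

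**Conclusion.** The point holds, at low severity. For a subject whose only SD precedes the 6-week minimum and whose later assessment is NE, Table 16.1 assigns PD that was not observed. If Any includes no later assessment, the same applies there. This conflicts with Appendix J and with the neighboring rows, and it is not declared as a change.

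The consequence is a PD-versus-NE label in the best-response tables and two plots. A reader might infer that the main Phase Ib activity result is biased. The documents do not support that: the primary endpoint is DLT incidence in Cycle 1, the listed efficacy endpoints are TTP, disease control, objective response, PFS, OS and AFP response, and the share of PD in the best-response table is not one of them.

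The percentages in the working are the weight of one subject at the planned maximum sizes, not an expected bias. The documents give no count of affected subjects; that there are few is a judgment from the narrow window and the continued scanning. The point is confined to the Phase Ib SAP, because Table 1 of the Phase II SAP, as available, has no SD row.

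**What to change.** Replace the SD / Any row of Table 16.1 with three rows:

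- **SD then PD:** SD if the minimum is met, otherwise PD.
- **SD then NE or no further assessment:** SD if the minimum is met, otherwise NE.
- **SD then SD, PR or CR:** a CR or PR confirmed under the table's rules stands. Failing that, SD if the minimum is met at any assessment of SD or better. Failing that, the later assessments decide, with NE rather than PD if no PD is observed.

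The third row is needed because Any now covers those sequences, and a split into the first two alone would leave them without a rule. Naming the case of no further assessment also settles what Any left open.

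The cost is an edit to one table and the matching derivation code. No new data are needed, and no other endpoint changes. If the sponsor wants to keep PD as a deliberate conservative rule, section 9 should list it with a reason, and the CR / NE and PR / NE rows should be reconciled with it.
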